7.1 Study Objectives

1. To evaluate the change in health related quality of life following CI treatment in elderly individuals by using the generic Health Utilities Index Mark III (HUI 3) assessment scale prospectively.
2. To evaluate the impact of CI treatment on the domains that have impact on overall well-being and healthy aging in the elderly such as :
 - a) hearing ability and communication
 - b) dependency
 - c) cognition
 - d) falls
 - e) depression/mood
3. To identify the changes in healthcare resource utilisation following CI treatment compared to preimplant.

The hypotheses:

Primary hypothesis

CI implant treatment significantly improves **the overall health related quality of life** of elderly individuals compared to their preimplant condition as measured on the HUI-3.

Secondary hypothesis

CI treatment in the elderly significantly impacts the healthy aging domains and therefore overall well-being in addition to hearing function compared to the preimplant condition as measured on clinically standard evaluation tools in the geriatric and audiological fields.

Tertiary hypothesis

CI treatment has the potential to create cost savings from the perspective of health care payer(s), health care provider(s) and society, by reducing health care resource utilisation for bilaterally severe to profound hearing impaired adults over 60 years of age, post implant compared to their preimplant status.

8 Design of the observational study

8.1 General

A repeated measure, single-subject observational design will be used for assessment of the changes in health related quality of life and overall well-being as the primary end-point of the study, in which each subject acts as his/her own control. Subjects are evaluated subjectively at pre- and post-operative intervals that coincide with their routine visits to the clinic.

This study is observational as no additional intervention is applied to the CI recipient. Outcomes from routine practice and application of CI intervention are recorded through observational measures using clinically standard scales used widely in geriatrics and audiology.

The study design is multi-centre, and multi-language; Italian, French, Spanish, Arabic and Hebrew. Translations of questionnaires have been controlled for via a validated translation process, and thus enabling collation of the data gathered cross culturally. The implant clinics have been chosen due to their long standing history in providing cochlear implant intervention for the treatment of hearing impaired individuals and for their existing capacity to recruit and treat elderly CI candidates for the study within a reasonable time frame.

Each participating clinic is anticipated to recruit a minimum of 8 and a maximum of 20 subjects in total if not agreed differently

8.2 Overview to Assessment Schedule and Visits

Figure 3 below represents an overview of the evaluation visits for each enrolled subject, designed to coincide with routine clinical visits involved in provision of CI intervention. Each subject will be assessed during three visits while participating in the study, creating three data sets and evaluation points per subject. The full battery of tests will be repeated at each of the three visits.

[figure not shown]

Figure 3 Overview to evaluation schedule flow and visits for each enrolled subject.

8.2.1 Preimplant visit 1 = Pre1

Preimplant visit 1 corresponds to the first evaluation with the full assessment battery for each subject before surgery and corresponds to his/her absolute baseline.

- Preimplant assessment before implant surgery date \leq 2 months

8.2.2 Postimplant Visit 2 = Post1

Postimplant Visit 2, (Post 1) corresponds to the first assessment after implantation @ 12 months (+/- 1 month) post surgery.

- Postimplant assessment post surgery @ 12 months + 1 month.

8.2.3 Postimplant Visit 3 = Post2

Postimplant Visit 3, (Post 2) corresponds to the second assessment after implantation @ 18 months (+/- 1 month) post surgery.

- Postimplant assessment post surgery @ 18 months \pm 1 month.

8.3 Global Overview of Data Collection

Table 1 provides an overview of the standardly available assessment tools making up the test battery to be used at each evaluation Visit (1 to 3). The corresponding health domain(s) assessed by each evaluation tool, as referred to and described under the primary and secondary hypotheses are indicated. In addition to the evaluation tools listed below, customized case report forms to summarize the Patient Profile and Healthcare resource utilisation over time will be completed by the clinician for each enrolled subject. Table 2 illustrates for whom completion of each assessment is targeted and the schedule.

Table 1. Overview to Evaluation Tools and health domains assessed.

DOMAINS ↓	HUI-3	TUG	GDS-15	LS de Jong	iADL	HHIE-S	SSQ	CAP II	Speech Recognition Testing	MMSE, Trail B, DSST	Data Logging
	Health Utility Index Mark 3	The Timed Up and Go test	Geriatric Depression Scale	Loneliness test	Lawton Instrumental Activities of Daily Living Scale	Hearing Handicap Inventory for the Elderly	Speech, Spatial, and Qualities of Hearing	Categories of Auditory Performance	As per Routine Clinical practise	Mini-Mental State Examination, Trail B, DigitLetter Substitution	
Risk of Falls		x									
Mobility	x										
Hearing & Communication	x					x	x		Testing in Quiet and Noise for CI only and CI + contralateral ear		x (usage)
Communication	x										x (envir.)
Social Isolation				x			x				
Dependence					x						
Mood/ Depression	x		x	x							
Cognition	x									x	
Time to complete (mins)	15	3	7	1	5	5	30	2	30	17	NA

Quality of Life, overall Health & Health Utility – HUI-3 (Vision, Hearing, Speech, Ambulation, Dexterity, Emotion, Cognition & Pain)

Hearing Ability – SSQ, Speech Recognition Testing, CAP II; Impact of Hearing on daily life – HHIE & SSQ,

Cognition – MMSE, Physical Balance - TUG (& VEMPS if routine), LS- Loneliness scale, DSST- Digit symbol substitution test, Trail B , Trail making task B.

Table 2 Evaluations by Visit by Clinician and by Candidate/Recipient

	Pre1	Post1	Post 2
Visits	Visit1	Visit2	Visit3
Questionnaires filled by clinicians using patient hospital files and/or interview			
Patient Profile	x	x	x
Societal Cost	x	x	x
CAP2	x	x	x
i-ADL	x	x	x
De Jong Loneliness	x	x	x
Self assessment Questionnaires			
HUI-3	x	x	x
GDS-15	x	x	x
HHIE-S	x	x	x
SSQ	x	x	x
Routine audiological assessments			
PTA	x	x	x
SFT	x	x	x
Speech in Quiet	x	x	x
Speech in noise	x	x	x
Routine Geriatric assessments			
DSST	x	x	x
Trail B	x	x	x
MMSE	x	x	x
TUG	x	x	x

8.4 End-points

Primary end-point

Change in overall health related quality of life via comparison of HUI3 multi-attribute utility scores at:

- **Post1** implant Visit compared to **Pre1** implant Visit
- **Post2** implant Visit compared to **Post1** implant Visit
- **Post2** implant Visit compared to **Pre1** implant Visit

Secondary end-points:

Change in scores on battery of evaluation tools for health related domains and overall well-being on each of the following:

MMSE, DSST & Trail B (Cognition); TUG (falls); GDS-15 (depression); iADL (independency); HHIE-S (hearing handicap); SSQ (hearing & communication ability); CAP-II (capabilities of audition); De Jong Loneliness Scale, Speech recognition tests in Quiet (daily hearing function); Speech recognition tests in Noise (daily hearing function); Consistent daily use of CI via automatic data logging (hrs/day and listening environments).

- **Post1** implant Visit compared to **Pre1** implant Visit
- **Post2** implant Visit compared to **Post1** implant Visit
- **Post2** implant Visit compared to **Pre1** implant Visit

Tertiary end point:

Changes in healthcare resource utilisation with CI treatment compared to preimplant, collected at each test interval, i.e., Pre 1, Post1 and Post 2 will be compared. Each assessment will reflect a 6 month period immediately before assessment. Data reviewed for this measure will be obtained from the customized HRU questionnaire completed by the clinician on behalf of the subject (data sources available for use will be in accordance with regional guidelines).

8.5 Investigational device and comparator

No investigational device is used in the study design. Only approved products for market release are used for routine CI treatment during the course of the observational study.

Each subject will act as their own control. As such the comparator for all subjects will be their daily preimplant listening situation.

8.6 Subjects

8.6.1 Inclusion Criteria

- Unilateral CI candidates with bilateral postlingual deafness with intention to treat
- ≥ 60 years at *first* unilateral cochlear implant
- Implant ear: meets all local criteria for CI treatment
- Contralateral ear: average pure tone thresholds indicate a moderately-severe to profound hearing loss (4 freq. average: 0.5, 1, 2 and 3 or 4 kHz >56 dBHL).
- Willingness to participate in and to comply with all study procedures
- Fluency in languages used to assess clinical performance
- Appropriate expectations from routine CI treatment
- Able to decide on study participation personally and independently sign their consent

8.6.2 Exclusion Criteria

- Significantly/severely dependent or fragile
- Unable to provide consent personally
- Unable to complete questionnaires for self-assessment independently
- Unilateral hearing loss
- Sequential and simultaneous bilateral cochlear implant recipients
- Ossification or other cochlear anomalies preventing full electrode insertion
- Retro cochlear or central origins of hearing impairment.
- Significant comorbidities preventing study participation (e.g. blindness, immobility or in a wheel chair, severe aphasia,..)
- Medical contraindications to surgery
- Clinically standard fail criteria for CI candidacy in regards to chronic depression, dementia, and cognitive disorders.
- Unrealistic expectations on the part of the subject, regarding the possible benefits, risks and limitations that are inherent to the procedure and prosthetic device.

8.6.3 Criteria and procedures for subject's withdrawal or discontinuation

Subjects can decide to withdraw from the investigation without indicating any reasons at any time. The patient will then continue to be managed by the clinic as per the routine clinical practice with the intention to treat the hearing impairment accordingly.

The investigator may decide to discontinue a patient due to major non-compliance with the Observational Study Protocol requirements (e.g. three-visit schedule not met) or in the event

the patient demonstrates rapid decline in overall health and is unable to participate in the study procedures.

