8.6.7 Number of subjects required to be included in the clinical investigation

The number of subjects to be enrolled will be **N=100** subjects across the seven investigator implant sites.

In view of possible attrition rate of 5 to 10 % of enrolled subjects, randomly lost to follow up during the course of the study any time after enrolment, all subjects enrolled will be included in the final analysis as the “intention to treat” cohort with the majority being assessed “as per protocol”.

The number of subjects recruited per site will reflect the local normal practices for treatment in the elderly population during the study enrolment time frame of 24 months. The study will aim to accrue subjects distributed across all study sites and languages to avoid site and cultural bias.

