Data collection will be performed using eCRFs within a validated and verified electronic data capture system (EDC) with role based security and unique login credentials for each individual user. Site personnel will be trained on the completion of the eCRFs. The investigator will confirm data accuracy by providing an electronic signature.

Data will be collected, stored and analysed in a secure manner in compliance with 21 CFR Part 11 and privacy regulations.

The EDC has built-in edit checks and will generate automated data clarification forms (DCFs). The clinical project manager (CPM), monitor and data manager may review the data for medical, scientific and data integrity, and will create manual DCFs where appropriate. Responses to DCFs will be entered into the EDC, with updates to the study data where required.

Following completion of the study, investigators will be provided with the data for their site (e.g. on a CD-ROM) for national and site specific archiving requirements.

After the final clinical investigation report (CIR) has been approved the data will be stored on CD-ROM and archived with the trial master file at the sponsor's site. The data are stored for a period of 15 years.

11 Amendments to the Observational Study Protocol (CIP)

No changes in the study procedures shall be effected without mutual agreement of the investigator(s) and the Sponsor. All changes must be documented by a signed (CIP)

amendment. Substantial changes that impact the patient experience during the trial will require notification to the responsible Ethics Committee(s).

12 Deviations from the Observational Study Protocol

As an observational study, it is recommended that the investigator comply with the protocol as far as possible for all enrolled subjects. Protection of the subjects' rights, safety, privacy and well-being is always paramount throughout the study and at any time. Deviations to the study protocol shall be documented and reported to the Sponsor as soon as possible. The EC should be informed by the investigator as applicable.

13 Device accountability

Routine procedures for commercially implanted device registration and accompanying warranty are to be followed.

14 Statements of compliance

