7.1 Handling of Dropouts or Missing Data

All participants should be included in the analysis regardless of missing values and no imputation (for example, last value carried forward) should be utilised. All possible care should be taken to ensure that missing values are not encountered at baseline especially with respect to subgroups of interest. The analysis methods to be suggested in the following section take into account all available data and produce unbiased estimates of effect even in the presence of missing values.

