7.3 Statistical Analyses

Primary hypothesis analysis

If comparison between the HUI3 multi-attribute score from pre-surgery to only one follow-up time point is of interest then paired t-tests can be used. A check of the assumption that the change from pre-surgery is normally distributed should be performed. The distribution of change scores should be approximately symmetric. The disadvantage of this approach is that it uses only complete data at any given pair of time points

If all pairwise differences are of interest (as per the hypothesis) and the scatter plot of change over time appears (close to) linear then a linear mixed-effects model with a fixed effect of time (treated as a continuous variable) and a random effect for participant should be used to explain the change in response variable over time. Tukey pairwise differences between time points can be specified (we recommend using the *multcomp* package in R as it does not require balanced designs i.e. the same sample size across time points). Appropriate diagnostic checks of the linear mixed-effects model (for example, normality of the residuals, normality of the random effects) should always be undertaken. An advantage of the linear mixed-effects model is that it uses all available data even for subjects who have dropped out at a given time point and then returned.

If the change over time was evidently not linear from the scatterplot of response against time then alternative approaches should be used. For example:

1. A quadratic or cubic term for time could be added to the linear mixed-effects model and checked to determine if that improves the fit of the model (eg via reduced AIC, better diagnostic checks).
2. The pre-surgery HUI3 multi attribute score value can be used as a predictor variable (with the response variable then only including the post-surgery visits). A significant coefficient would imply that the amount of change is dependent on the pre-surgery score. An interaction between baseline score and post-surgery time points could also be included – this would show whether the change in mean score over time is impacted by baseline score. This approach will remove any participant without baseline data from the analysis.

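### Protocol 8.6.3 allows a subject to be discontinued for not meeting the visit schedule, so 18-month HUI3 data that could be obtained may be lost at the investigator's discretion

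*Protocol*

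**What the plan says.** Protocol 8.6.3 says that the investigator may discontinue a subject for "major non-compliance with the Observational Study Protocol requirements (e.g. three-visit schedule not met"). The same sentence has a second, separate ground: rapid decline in health that leaves the subject unable to take part.

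The schedule in question is three visits. Visit 2 "corresponds to the first assessment after implantation @ 12 months (+/- 1 month) post surgery" and Visit 3 "corresponds to the second assessment after implantation @ 18 months (+/- 1 month) post surgery".

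Other parts of the plan deal with incomplete schedules as follows:

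- Protocol 8.6.7: "all subjects enrolled will be included in the final analysis as the “intention to treat” cohort". It expects 5 to 10% attrition and describes it as random.
- Protocol section 12: "it is recommended that the investigator comply with the protocol as far as possible for all enrolled subjects". Deviations are to be documented and reported to the sponsor.
- SAP 7.1: "All participants should be included in the analysis regardless of missing values and no imputation (for example, last value carried forward) should be utilised".
- SAP 7.3, on an advantage of the mixed model: "it uses all available data even for subjects who have dropped out at a given time point and then returned".

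Neither document says whether a subject with a missed or out-of-window visit is still to be invited to the next one.

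**The concern.** The analysis rules protect only data that exist. SAP 7.1 and the mixed model can use an 18-month score from someone who missed the 12-month visit, but only if that score was collected. Protocol 8.6.3 gives the site a stated reason to stop before then.

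The clause is discretionary and its threshold is undefined. The same event could end participation at one site and be recorded as a deviation at another. Whether an 18-month score exists then depends partly on who made the decision, and the decision follows an event that may itself be related to how the subject is doing. That is harder to describe as random loss. At stake is the 18-month part of the primary endpoint, both in the number of pairs and in whether the subjects who remain represent those enrolled.

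**Working it through.** **1. What one removal costs.** Protocol 8.4 lists three HUI3 contrasts: Post1 vs Pre1, Post2 vs Post1, and Post2 vs Pre1. Post2 is in two of them.

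- 12-month visit missed, subject removed: both contrasts involving Post1 already lack a pair. Removal additionally costs the Pre1–Post2 pair and leaves only Pre1 in the model.
- 12-month visit late but done, subject then removed: Pre1 and Post1 stay in the model, and both Post2 pairs are lost.

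**2. Reproducing the plan's sample sizes.** Inputs from SAP section 5: change 0.1, SD of change 0.25, 90% power. The test is a two-sided paired t-test (Protocol section 9). Power is P(|T| > t at 1 − α/2 with n − 1 df), where T is noncentral t with noncentrality (0.1/0.25)√n = 0.4√n.

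- α = 0.05: smallest n is 68, which matches the plan.
- α = 0.05/3 = 0.0167: smallest n is 88, which matches the plan.

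**3. Reserve in the planned 100.** Enrolment needed to retain 88 is 88/0.95 = 92.6, so 93, at 5% attrition, and 88/0.90 = 97.8, so 98, at 10%. At 10% attrition the reserve is 2 subjects.

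**4. Further loss of Pre1–Post2 pairs.** The documents give no rate, so 5 to 15 is an assumption. The starting point is 100 × 0.90 = 90.

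| Further pairs lost | Pairs left | Power, α = 0.0167 | Power, α = 0.05 |
|---|---|---|---|
| 0 | 90 | 91.0% | 96.4% |
| 5 | 85 | 89.1% | 95.4% |
| 10 | 80 | 86.8% | 94.2% |
| 15 | 75 | 84.2% | 92.8% |

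These are powers for one paired comparison. The SAP's mixed model would also use the earlier data of removed subjects.

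**5. Selective loss.** Let a share f lack 18-month data, and let their true mean change be lower by d than that of the subjects observed. The mean over everyone is then the observed mean − f × d, so the observed mean is too high by f × d. Illustrative values, all assumed:

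- f = 5%, d = 0.10: 0.05 × 0.10 = 0.005
- f = 10%, d = 0.10: 0.10 × 0.10 = 0.010
- f = 15%, d = 0.165: 0.15 × 0.165 = 0.025

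The value 0.165 is the mean gain in the earlier data set cited in Protocol section 9. The last line therefore corresponds to no gain at all in the lost subjects if the others gained that much. The protocol's minimum important change is 0.03. The formula describes an analysis of observed pairs. A mixed model can reduce the bias where earlier scores predict the loss, but a subject with only Pre1 gives it little to work with.

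**The case against.** The strongest reply is that the clause is permissive and limited to *major* non-compliance. A slightly late visit need not trigger it, and nothing shows that sites will use it. This stands, and it rules out several stronger readings that a reader might infer:

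- *Missing a visit means removal.* The text says 'may'.
- *Section 12 contradicts 8.6.3.* It does not. Documenting every deviation and allowing removal for major ones are compatible tiers.
- *Late assessments are rejected.* Neither document says so.
- *The intention-to-treat cohort turns into a cohort of schedule-compliers, and the mixed model's advantage is lost.* Removed subjects stay in the analysis with the data they gave. The advantage remains for anyone who misses a visit and is kept.
- *The SAP depends on returning subjects.* It names their use as one advantage of the model.

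Two more points stand. The 5 to 10% attrition in 8.6.7 covers loss at any time after enrolment and might already include schedule-based removals, so adding further losses may double count. Visit handling may also be set out in the separate Procedure document or Monitoring Plan, which are not available here.

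What the reply does not remove is the gap itself. The only example of major non-compliance is an unmet schedule, the threshold is undefined, and neither document keeps the subject in follow-up. Subjects too unwell to take part are already covered by the separate health ground, so the schedule example mainly adds people who might still attend.

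**Conclusion.** The point holds as a permitted and avoidable loss of data. It does not show that data will be lost. Protocol 8.6.3 works against the aims of Protocol 8.6.7 and of SAP 7.1 and 7.3, and it allows practice to differ between sites.

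The effect on power is modest. Even 75 pairs exceed the protocol's 68 and give 92.8% power at α = 0.05, although they fall short of the SAP's 88 at α = 0.0167. The main concern is selective loss: roughly 0.005 to 0.025 HUI3 units in the examples above, below but not negligible beside the 0.03 threshold. Those figures rest entirely on assumed rates and differences. The documents give neither a rate of schedule-based removal nor reasons for missed visits. This is worth changing because the remedy is simple; it does not invalidate the design.

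**What to change.** - In Protocol 8.6.3, delete the parenthetical example of the unmet three-visit schedule.
- State that a missed or out-of-window visit is documented as a deviation under section 12, is not by itself a ground for ending study follow-up, and that the subject is still invited to every later visit.
- Record the actual date of each assessment. Analyse all collected data in the intention-to-treat cohort, and use the ±1 month windows only to define a per-protocol sensitivity analysis. Add matching text to the SAP.
- Leave the separate health-decline ground in place, but reconcile its wording with section 17. Protocol 8.6.3 makes that removal optional and ties it to being unable to participate. Section 17 says the clinician should remove the subject once decline prevents comfortable participation. The sponsor and investigators must settle which applies.

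Cost: a signed protocol amendment (Protocol section 11), with ethics committee notification where applicable, a short SAP addition, and some assessments outside the nominal window. Protocol section 6 states that study visits coincide with routine management, so continued assessment should add no extra clinic visit.
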